9.1 Adverse events

Information about all adverse events, whether volunteered by the subject, discovered by investigator questioning, or detected through physical examination, laboratory test or other means, will be collected and recorded and followed as appropriate.

An adverse event is the appearance or worsening of any undesirable sign, symptom, or medical condition occurring after starting the study drug even if the event is not considered to be related to study drug. Medical conditions/diseases present before starting study drug are only considered adverse events if they worsen after starting study drug. Abnormal laboratory

values or test results constitute adverse events only if they induce clinical signs or symptoms, are considered clinically significant, or require therapy.

The occurrence of adverse events should be sought by non-directive questioning of the patient at each visit during the study. Adverse events also may be detected when they are volunteered by the patient during or between visits or through physical examination, laboratory test, or other assessments. As far as possible, each adverse event should be evaluated to determine:

1. the severity grade (mild, moderate, severe) or (grade 1-4)
2. its relationship to the study drug(s) (suspected/not suspected)
3. its duration (start and end dates or if continuing at final exam)
4. action taken (no action taken; study drug dosage adjusted/temporarily interrupted; study drug permanently discontinued due to this adverse event; concomitant medication taken; non-drug therapy given; hospitalization/prolonged hospitalization)
5. whether it constitutes a serious adverse event (SAE)

All adverse events should be treated appropriately. Such treatment may include changes in study drug treatment including possible interruption or discontinuation, starting or stopping concomitant treatments, changes in the frequency or nature of assessments, hospitalization, or any other medically required intervention. Once an adverse event is detected, it should be followed until its resolution, and assessment should be made at each visit (or more frequently, if necessary) of any changes in severity, the suspected relationship to the study drug, the interventions required to treat it, and the outcome.

Information about common side effects already known about the investigational drug can be found in the Investigators' Brochure or will be communicated between IB updates in the form of Investigator Notifications. This information will be included in the patient informed consent and should be discussed with the patient during the study as needed.

9.1.1 Serious adverse events

Information about all serious adverse events will be collected and recorded. To ensure patient safety each serious adverse event must also be reported to Recordati Inc. within 24 hours of learning of its occurrence. A serious adverse event is an undesirable sign, symptom or medical condition which:

- is fatal or life-threatening
- results in persistent or significant disability/incapacity
- constitutes a congenital anomaly/birth defect
- requires inpatient hospitalization or prolongation of existing hospitalization, unless hospitalization is for:
 - routine treatment or monitoring of the studied indication, not associated with any deterioration in condition (specify what this includes)
 - elective or pre-planned treatment for a pre-existing condition that is unrelated to the indication under study and has not worsened since the start of study drug
 - treatment on an emergency outpatient basis for an event not fulfilling any of the definitions of a SAE given above and not resulting in hospital admission

- social reasons and respite care in the absence of any deterioration in the patient's general condition
- is medically significant, i.e., defined as an event that jeopardizes the patient or may require medical or surgical intervention to prevent one of the outcomes listed above

9.1.2 Recordati Inc. instructions for rapid notification of serious adverse events

The principal investigator has the obligation to report all serious adverse events to the FDA, IRB, and Recordati Inc. Pharmaceuticals Integrated Medical Safety (IMS).

All events reported to the FDA by the investigator are to be filed utilizing the Form FDA 3500A (MedWatch Form).

All events must be reported, by [contact]), to Recordati Inc. Pharmaceuticals IMS Department within 24 hours of learning of its occurrence. This includes serious, related, labeled (expected) and serious, related, unlabeled (unexpected) adverse experiences, all deaths during treatment or within 30 days following completion of active protocol therapy.

Any serious adverse event occurring after the patient has provided informed consent and until 4 weeks after the patient has stopped study participation must be reported. This includes the period in which the study protocol interferes with the standard medical treatment given to a patient (e.g. treatment withdrawal during washout period, change in treatment to a fixed dose of concomitant medication).

Serious adverse events occurring more than 4 weeks after study discontinuation need only be reported if a relationship to the Recordati Inc. study drug (or therapy) is suspected.

For Comparator Drugs/Secondary Suspects (Concomitant Medications), all serious adverse experiences will be forwarded to the product manufacturer by the investigator.

9.1.3 Pregnancies

Any pregnancy that occurs during study participation should be reported. To ensure patient safety each pregnancy must also be reported to Recordati Inc. within 24 hours of learning of its occurrence. The pregnancy should be followed up to determine outcome, including spontaneous or voluntary termination, details of birth, and the presence or absence of any birth defects, congenital abnormalities or maternal and newborn complications.

9.2 Data Monitoring Board

The participating investigator will report all adverse events and serious adverse events to the Principal Investigator (or Protocol Chair) and to the IRB according to the local IRB's policies and procedures in reporting adverse events.

10 Data collection

Once eligibility has been established and the participant successfully registered, the participant is assigned a protocol case number. This number is unique to the participant on this trial and must be used for case report form (CRF) completion.

Investigators must enter the information required by the protocol onto CRFs.

11 Statistical methods and data analysis

11.1 Sample size

35 patients will be enrolled, with up to 3 additional patients to account for potential dropouts.

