The primary efficacy endpoint is progression-free survival, defined as the time from the date of first study treatment to the date of the first documented disease progression (by RECIST criteria) or death due to any cause. If a patient has not progressed or died at the date of the analysis cut-off or when he/she receives any further anti-cancer therapy, PFS is censored at the time of the last tumor assessment before the cut-off or the anti-cancer therapy date.

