8.4 PFS and Censoring

Since disease progression is assessed periodically, the true date of disease progression is known only to occur at a time point after the last radiological assessment of stable disease (or better) and prior to the date of the scan detecting progression. Table 8.4 provides instructions on classification of the primary endpoint (PFS) depending on various clinical scenarios.

Table 8.4: Classification of Primary Outcome

Situation	Outcome	Date of Progression or Censoring
Progression documented between scheduled visits	Progressed	Earliest of: Date of radiologic assessment showing new lesion (if progression is based on new lesion); or Date of last radiologic assessment of measured lesions (if progression is based on increase in sum of measured lesions)
No progression	Censored	Date of last radiologic assessment of measured lesions
Treatment discontinuation for undocumented progression	Censored	Date of last radiologic assessment of measured lesions
Treatment discontinuation for	Censored	Date of last radiologic assessment of

toxicity or other reason		measured lesions
New anticancer treatment started	Censored	Date of last radiologic assessment of measured lesions
Death before first progressive disease assessment	Progressed	Date of death
Death between adequate assessment visits	Progressed	Date of death
Death after one to two missed visits	Progressed	Date of death
Progression after one to two missed visits	Progressed	Earliest of: Date of radiologic assessment showing new lesion (if progression is based on new lesion); or Date of last radiologic assessment of measured lesions (if progression is based on increase in sum of measured lesions)
Death or progression after more than two missed visits	Censored	Date of last radiologic assessment of measured lesions

9 Safety monitoring

Safety assessments will consist of monitoring and recording all adverse events and serious adverse events, the regular monitoring of hematology and blood chemistry parameters and regular physical examinations. Adverse events will be evaluated continuously throughout the study. Safety and tolerability will be assessed according to the NIH/NCI Common Terminology Criteria for Adverse Events version 4.0 (CTCAE v4.0) that is available at:

<http://evs.nci.nih.gov/ftp1/CTCAE/About.html>

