11.2 Sample size justification

We plan to conduct a single-arm phase II trial, with the 12-month progression-free survival rate as the primary endpoint, and using a one-sided alpha level of 10%.

The null hypothesis is that PFS rate at 12 months will be 19%. With n=30 (plus up to 3 additional patients (10%) to account for early dropouts), we will have 90% power to reject the null, if the true 1-year PFS rate from this treatment regimen is 40% (these PFS rates correspond to null and alternative hypothesis median PFS of 5 and 9 months, respectively). The sample size calculations were conducted using nQuery Advisor 6.01.

The sample size was derived for the estimation of PFS at 1-year using binomial theory. If the survival distribution is exponential, a much tighter confidence interval for the 1-year survival is possible. We will first test for the exponentiality of the survival distribution using the Hollander=Proschan¹⁷ test. If the p-value for this preliminary test is greater than 0.20, we will provide the 90% lower confidence bound assuming an exponential distribution.

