Any change or addition (excluding administrative) to this protocol requires a written protocol amendment that must be reviewed by Recordati Inc. and the investigator before implementation. Amendments significantly affecting the safety of subjects, the scope of the investigation or the scientific quality of the study require additional approval by the IRB at each study center. A copy of the written approval of the IRB must be provided to Recordati Inc. Examples of amendments requiring such approval are:

1. increases in drug dose or duration of exposure of subjects,
2. significant changes in the study design (e.g. addition or deletion of a control group),
3. increases in the number of invasive procedures,
4. addition or deletions of a test procedure required for monitoring of safety.

These requirements for approval should in no way prevent any immediate action from being taken by the investigator or by Recordati Inc. in the interests of preserving the safety of all patients included in the trial. If an immediate change to the protocol is felt to be necessary by the investigator and is implemented for safety reasons Recordati Inc. must be notified and the IRB at the center must be informed immediately.

15 Procedures and Instructions

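### Sections 11.1 and 11.2 give different sample sizes (35 plus up to 3, against 30 plus up to 3), and the 90% power is stated only for 30

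*Combined protocol and SAP*

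**What the plan says.** Section 11.1 (Sample size) is one sentence: "35 patients will be enrolled, with up to 3 additional patients to account for potential dropouts". Accrual therefore ends at 38 at most.

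Section 11.2 (Sample size justification) describes a single-arm trial with the 12-month PFS rate as primary endpoint, one-sided alpha of 10%, a null rate of 19% and an alternative of 40%. It then says "With n=30 (plus up to 3 additional patients (10%) to account for early dropouts), we will have 90% power to reject the null". Accrual therefore ends at 33 at most. It adds that "these PFS rates correspond to null and alternative hypothesis median PFS of 5 and 9 months, respectively", and that "The sample size was derived for the estimation of PFS at 1-year using binomial theory".

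Section 11.2 does not say whether the binomial test is exact or approximate, and it gives no number of progression-free patients that would reject the null. Neither section derives 35 or gives a power for it.

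**The concern.** The section headed as a justification justifies a different number from the one it follows. Three things hang on this.

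- Sites and ethics committees cannot tell whether accrual stops at 33 or at 38.
- The size to be enrolled has no power statement, and the size with a power statement is not the one enrolled.
- In a single-arm trial judged on a count of progression-free patients, the required count depends on the number analysed. With two sizes, an unnamed test and no stated count, the rule could be settled after the results are known.

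**Working it through.** **Inputs (Section 11.2).** One-sided alpha 0.10; null p0 = 0.19; alternative p1 = 0.40; medians 5 and 9 months; n = 30. From Section 11.1: n = 35, maximum 38.

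**Rates behind the medians.** Assuming exponential PFS, the 12-month rate is 0.5^(12/median): 0.5^(12/5) = 0.1895 and 0.5^(12/9) = 0.3969. These round to the stated 19% and 40%.

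**Reproducing the 90% at n = 30.**

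1. Normal approximation at 19%/40%. The critical proportion is p0 + 1.2816 × sqrt(p0(1 − p0)/n) = 0.19 + 1.2816 × 0.0716 = 0.2818. Power is Φ[(0.40 − 0.2818)/sqrt(0.40 × 0.60/30)] = Φ(0.1182/0.0894) = Φ(1.32) = 90.7%. Reproduced.
2. Exact binomial at the median-implied rates. P(X ≥ 9 | 30, 0.1895) = 9.9% and P(X ≥ 9 | 30, 0.3969) = 90.0%. Reproduced.
3. Strict exact binomial at the stated 19%/40%. P(X ≥ 9 | 30, 0.19) = 10.04%, just over the limit, so 10 are needed: alpha 4.5%, power 82.4%. Not reproduced.

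**Can 30 become 35 through dropouts?** 30 + 3 = 33. 30/0.9 = 33.3, rounded up to 34. The 10% label fits 3/30 = 10.0% but not 3/35 = 8.6%. Section 11.1 also adds its own 3 on top of 35, so 35 is not a dropout-inflated 30.

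**Power and success count by number analysed, 19%/40%, one-sided 10%.** The strict exact rule is the smallest count r with P(X ≥ r | n, 0.19) ≤ 0.10.

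| n | r | exact alpha | exact power | normal-approximation power |
|---|---|---|---|---|
| 30 | 10 | 4.5% | 82.4% | 90.7% |
| 31 | 10 | 5.6% | 85.7% | 91.3% |
| 32 | 10 | 6.8% | 88.4% | 91.9% |
| 33 | 10 | 8.1% | 90.8% | 92.5% |
| 34 | 10 | 9.6% | 92.7% | 93.0% |
| 35 | 11 | 5.5% | 88.8% | 93.4% |
| 36 | 11 | 6.6% | 91.0% | 93.9% |
| 37 | 11 | 7.8% | 92.8% | 94.3% |
| 38 | 11 | 9.2% | 94.3% | 94.7% |

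At 35, a count of 10 would have alpha 11.3%, which is why 11 are needed. The required count steps from 10 to 11 between 34 and 35, which is between the two sections' maxima. At the median-implied rates the counts for 31 to 38 are the same; only n = 30 differs (9 instead of 10).

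**The case against.** The best defence is that the mismatch does little harm. If 35 is enrolled, power is about 88% to 93% depending on the test, close to or above the stated 90%, and the extra patients cost the design nothing in sensitivity. That stands. A reader might infer from the contradiction that the trial is underpowered, and the documents do not support that.

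A reader might also infer that the 90% is right for 30 and wrong for every other size. That does not hold either. By strict exact test at the stated rates, 30 gives 82.4%, while 33 gives 90.8% and 36 gives 91.0%. By normal approximation, 29 already gives 90.0%. Which size matches 90% depends on the test, and Section 11.2 says only that binomial theory was used. What can be said is that 90% is stated only for 30, and that it reproduces there by two standard routes and fails by a third.

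Two nearby questions are separate: what role the exponential confidence bound in Section 11.2 plays, and how patients censored before 12 months under Table 8.4 enter a binomial count. Neither follows from 35 against 30, and correcting the mismatch does not require settling them.

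A final objection concerns the remedy. The trial is open-label (Section 4) and single-arm (Section 11.2), and Section 7.2 already sets visit rules for patients on therapy beyond five years. The documents do not state accrual status. If 12-month outcomes are already known, choosing a size and success count now would be a data-driven choice. That stands, and the fix must guard against it.

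**Conclusion.** The sample size is wrong as written: two sections give two sizes (maximum 38 against 33), nothing reconciles them, and the only power figure belongs to the smaller. The loss of power is small or nil: at 19%/40% and n = 35, power is 88.8% by strict exact test (at least 11 of 35, alpha 5.5%) and 93.4% by normal approximation. The harm is an unclear accrual limit and an undefined decision rule. Under a strict exact test at 19%, the same 10 progression-free patients reject the null with 31 to 34 analysed and fail to with 35 to 38.

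The contradiction needs no assumption. The power figures assume that each analysed patient's 12-month status is known. The median-implied rates assume exponential PFS.

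**What to change.** State one evaluable number and one enrolment maximum, the same in 11.1 and 11.2, with the named test, alpha, power and success count, all on one set of rates. Use the size the design intended, and settle it without reference to 12-month outcomes. If those outcomes are already known, say so and report the rule as set afterwards.

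**If 35 is the intended size** (exact one-sided test at 10%, 19% against 40%): 35 evaluable, up to 38 enrolled (3/35 = 8.6%), reject at 11 or more. That count serves every size from 35 to 38, with the alpha and power in the table above. Restate the 90% as 88.8% at n = 35.

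**If 30 is the intended size:** correct 11.1 to 30 evaluable, up to 33 enrolled, and choose one of these:

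- Name the normal-approximation test, power 90.7% at 19%/40%. Its cut is 0.2818 × 30 = 8.45, so at least 9 of 30; the exact alpha of that rule is 10.04%.
- Use the exact test with the null written as 18.95% and the alternative as 39.69%. Count, alpha and power are then: 30, at least 9, 9.9%/90.0%; 31, at least 10, 5.5%/84.8%; 32, at least 10, 6.7%/87.7%; 33, at least 10, 8.0%/90.2%.

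The cost is one amendment, since Section 14 says "Any change or addition (excluding administrative) to this protocol requires a written protocol amendment". No patients are needed beyond the 38 already in 11.1. The downside is that the stated power may become slightly less favourable, as with 88.8% at n = 35.

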11.2 Sample size justification

We plan to conduct a single-arm phase II trial, with the 12-month progression-free survival rate as the primary endpoint, and using a one-sided alpha level of 10%.

The null hypothesis is that PFS rate at 12 months will be 19%. With n=30 (plus up to 3 additional patients (10%) to account for early dropouts), we will have 90% power to reject the null, if the true 1-year PFS rate from this treatment regimen is 40% (these PFS rates correspond to null and alternative hypothesis median PFS of 5 and 9 months, respectively). The sample size calculations were conducted using nQuery Advisor 6.01.

The sample size was derived for the estimation of PFS at 1-year using binomial theory. If the survival distribution is exponential, a much tighter confidence interval for the 1-year survival is possible. We will first test for the exponentiality of the survival distribution using the Hollander=Proschan¹⁷ test. If the p-value for this preliminary test is greater than 0.20, we will provide the 90% lower confidence bound assuming an exponential distribution.

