7.2 Evaluations During Treatment

Beginning of every cycle (defined as 28 days +/- 3 days) (every 6 months after 5 years on therapy)

- Physical examination
- Toxicity assessment
- Vital signs
- ECOG performance status
- CBC with differential
- Fasting comprehensive metabolic panel
- Assessment of adverse events

Data to be obtained every 3 cycles of treatment (every 12 months after 5 years on therapy):

- Radiologic assessment of tumor burden by CT scan or MRI. Patients who have been on study for > 2 years will undergo scans every 6 cycles. Patients who have been on study for > 5 years will undergo scans every 12 cycles, at treating physician discretion.
- Electrocardiogram (baseline, 6 hours after 1st injection, 21 days after 1st injection, 21 days after 3rd injection, Cycle 6, and every 3 cycles thereafter.)
- Liver function testing 21 days after 1st injection and 21 days after 3rd injection
- Assessment of chromogranin A and/or other tumor markers or hormones if elevated at baseline (see section 7.1).
- EORTC QLQ C-30 and EORTC QLQ GI-NET21 questionnaires

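### The exponential 90% lower bound for 12-month PFS in Section 11.2 treats scan-detection dates as exact event times, so near the 19% null it sits too high and under-covers, chiefly when few events are deaths

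*Combined protocol and SAP*

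**What the plan says.** Section 11.2 sets a one-sided 10% level, a null 12-month PFS of 19% and an alternative of 40%, and derives n = 30 from binomial theory. It then says "If the survival distribution is exponential, a much tighter confidence interval for the 1-year survival is possible", plans a goodness-of-fit pretest, and continues: "If the p-value for this preliminary test is greater than 0.20, we will provide the 90% lower confidence bound assuming an exponential distribution". No likelihood or bound formula is given.

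On dating, Section 8 runs PFS to the "date of the first documented disease progression (by RECIST criteria) or death due to any cause", with patients who have no event censored at their last tumor assessment. Section 8.4 acknowledges that "the true date of disease progression is known only to occur at a time point after the last radiological assessment of stable disease" and before the scan that detects it. Table 8.4 nevertheless assigns one date: a radiologic assessment date for progression, the date of death for deaths.

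On the scan schedule, Section 7.2 places imaging under "Data to be obtained every 3 cycles of treatment", which is 84 days with 28-day cycles, and adds "Patients who have been on study for > 2 years will undergo scans every 6 cycles". After five years the interval is 12 cycles.

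On the target, 11.2 states its power "if the true 1-year PFS rate from this treatment regimen is 40"%, whereas Section 8 defines PFS by documented progression.

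**The concern.** An exponential fit estimates the hazard as events divided by total observed time. If each progression is dated at the scan that found it, every such time is too long by the gap between the true event and the next scan. The hazard is then underestimated and the 12-month rate overstated. Enrolling more patients does not remove this; it narrows the bound around the wrong value.

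In a single-arm trial, readers will set the reported 12-month rate and its lower bound beside 19%. The plan presents the exponential interval as the sharper one. If it is centred too high near the null, a regimen with a true rate of 19% can appear to exceed the benchmark more often than a 90% bound implies.

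**Working it through.** **Plan's own figure.** For X ~ Binomial(30, p), P(X ≥ 9) is 0.1004 at p = 0.19 and 0.906 at p = 0.40. The stated 10% level and 90% power are reproduced, and the sizing is not in question.

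**Inputs from the document.** Null 19%, alternative 40%, one-sided 90% bound (11.2); n = 30 (11.2) and 35 (11.1), both run; 28-day cycles (4.1); scans every 3 cycles, then every 6 after two years (7.2); event and censoring dates (8, 8.4).

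**Assumptions not in the document.** Exponential PFS; uniform 24-month accrual; at least 12 months of follow-up; 0, 25 or 50% of events being exactly dated deaths; bound exp(−12·χ²₀.₉₀/(2T)) with 2D or 2D+2 degrees of freedom, where D is events and T total time. The pretest is left out of the main runs.

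**Limiting bias, no deaths.** With g = 84/30.4375 = 2.76 months, the mean scan-dated time is g/(1 − exp(−λg)).

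- True 19%: λ = −ln(0.19)/12 = 0.1384 per month. The mean goes from 7.23 to 8.69 months, and the fit tends to exp(−12/8.69) = 25.1%.
- True 40%: λ = 0.0764. The mean goes from 13.10 to 14.52 months, and the fit tends to exp(−12/14.52) = 43.8%.

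**Scan-documented target.** Status at 12 months is last known from the week-48 scan (4 × 2.76 = 11.04 months). With death share d, the documented rate is exp(−11.04λ)·[1 − d(1 − exp(−0.96λ))]. A true 19% with no deaths gives 21.7% documented. A documented 19% needs λ = 0.1504, 0.1474 or 0.1444 for d = 0, 25 or 50%.

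**Simulation** (40,000 trials per cell). Share of trials in which the bound lies above the target; nominal value 10%:

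| Target | Deaths | Mean fit | 2D | 2D+2 |
|---|---|---|---|---|
| True 19% | 0 | 25% | 39-42% | 31-34% |
| True 19% | 25% | 23.5% | 29-31% | 22-25% |
| True 19% | 50% | 22% | 20-22% | 15-17% |
| True 40% | 0 | 44% | 21-23% | 15-18% |
| True 40% | 25% | 42% | 17-18% | 12-13% |
| True 40% | 50% | 41% | 13-14% | 9-10% |
| Documented 19% | 0 | 23% | 23-25% | 17-19% |
| Documented 19% | 25% | 22% | 18-19% | 13-15% |
| Documented 19% | 50% | 21% | 14-15% | 10-11% |
| Documented 40% | 0-50% | 40-41% | 9-12% | 6-8% |

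With exact dates the same bounds miss in 10-11% (2D) or 7-8% (2D+2) of trials. Moving to 168-day scans after two years changes results by about 0.7 points at most. Varying accrual (6-36 months) and minimum follow-up (12-24 months) at a true 19% gives 30-45% with no deaths and 13-23% with half deaths. Wald and likelihood-ratio bounds, run with no deaths under other follow-up patterns, also under-cover the true rate: 60-70% coverage at 19% and 78-85% at 40%.

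**After the fix.** An interval-censored exponential likelihood averages 18.8-19.0% at a true 19%. Its likelihood-ratio bound misses in 8-10% of trials at both 19% and 40%.

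**The case against.** Five points weigh on the other side.

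- **PFS is defined by documented progression.** On that reading the detecting scan date is the event time, and the word true in 11.2 may be ordinary power language. This stands in part. It removes the problem at 40%, but not at 19% with few deaths, because a continuous exponential curve fitted to times that fall on an 84-day grid still misstates the documented rate there. A reader might infer that coverage is below 90% in general; the table does not support that.
- **The bound is an addition.** It follows a pretest, and 11.2 attaches no decision rule to it, while the sizing rests on the binomial test. This stands. A reader might take the 31-42% as the trial's false-positive rate. The document does not make this bound the decision rule, so the figures are miscoverage only.
- **The true-rate reading conflicts with the binomial test.** The 10.04% level holds only if 19% is a documented rate. If 19% were the true rate, the 9-of-30 rule would reject in 18.6% of trials with no deaths and 14.0% with half deaths. This stands, so the fix must not turn the bound into a second test of 19%.
- **Direction.** For some progressions Table 8.4 uses the last radiologic assessment of measured lesions. If that meant the scan before detection, the bias would reverse (19% fitted as about 14%, coverage 97-98%). The detecting scan is the natural reading, since Section 8 dates PFS at first documented progression, but the direction depends on it.
- **The pretest might screen out bad fits.** An approximate version (n = 35, staggered or long follow-up) passed 81-87% of trials at 19%, with coverage of 49-56% among those passing. The exact test was not reproduced, so this shows only that the pretest cannot be relied on as protection.

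**Conclusion.** The point holds in limited form. Section 11.2 has no step for interval censoring although Section 8.4 describes it, and on the natural reading of Table 8.4 the exponential fit is biased upward near the null. The fitted rate is about 6 points high at a true 19% with no deaths and about 3 points high when half the events are deaths. The shortfall shrinks as the rate rises, as the share of deaths rises, and when the target is the documented rate. It is about absent for a documented 19% with half deaths and the 2D+2 form, and absent or reversed for a documented 40%.

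These sizes rest on exponential PFS and on accrual, follow-up, death share and a bound formula that the document does not give. Confidence is high that the step is missing and medium on the size. It is worth correcting before analysis, because the bound will be read against 19% and the correction needs only wording.

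**What to change.** Add to Section 11.2:

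> The exponential estimate and 90% lower bound will be computed by interval-censored likelihood. Event and censoring status follow Table 8.4 unchanged, including censoring at new anticancer therapy and after more than two missed visits. Each progression counted as an event enters as occurring between the last scan without progression and the detecting scan; each death counted as an event enters on its date; censored patients enter at the last scan. The bound is labelled as an estimate of the true 12-month PFS rate. All other PFS analyses keep Table 8.4 dates.

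Also state that the binomial test against 19%, on which the sample size rests, decides the hypothesis, and that the exponential bound is supportive. Do not replace 19% with a null worked out from the observed share of deaths; that would set the hypothesis after the data are seen.

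**Cost.** No new scans or data are needed, since the bracketing scans are already scheduled assessments. The reported estimate and bound become less favourable, though at a true 40% the corrected bound still lies above 19% in 95-97% of trials. Two dating conventions must be labelled in the report. The bound still depends on the exponential assumption.
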